8.2.2.2 Visit windowing for other assessments

Visit windowing for months will be applied to gluten tests to determine an absence or presence of gluten. Refer to the SAP section on the primary estimand and handling of intercurrent events.

No analysis windows will be applied to Anti-TTG antibody IgA, Anti-DGP antibody IgA, IL-15 biomarkers, or safety assessments. By-visit analyses will be presented using the nominal time points.

8.2.2.3 Change from Baseline

Absolute change from baseline is defined as post-baseline value minus baseline value, i.e., a positive sign indicates an increase compared to baseline.

Percent change from baseline is defined as

[(post-baseline value – baseline value) / (baseline value)] x 100.

8.2.3 Imputing Missing Values

Primary Endpoint

Imputation of missing values for sensitivity analysis of the primary endpoint is described in detail in Section 8.6.1.3.

BSFS Stools of Type 6 or 7

Weekly scores are calculated by summing the previous 7 days. Missing days within a given week will be imputed as the average of the non-missing days for a given assessment week for the derivation

of weekly sums. Weekly score is calculated if there are at least 4 non-missing daily scores available. If there are less than 4 non-missing daily scores, weekly score will be counted as missing.

Laboratory Assessments

For all clinical laboratory assessments, values below the lower limit of quantitation (LLQ) will be assigned a value of 0.5 x LLQ for summary statistics and values over the upper limit of quantitation (ULQ) will be assigned a value of ULQ for summary statistics.

PK Concentrations

PRV-015 concentrations below the LLQ will be assigned a value of 0.5 x LLQ in mean calculations for the summary of PRV-015 concentrations.

Missing and Partial Dates

Missing dates for Adverse Events and Concomitant Medications

For completely missing AE or CM start dates, the following applies:

- If end date is missing or it is after the start of the DB treatment date, then the start of the DB treatment date is used.
- If end date is in the SB placebo run-in phase, the start date of the event is imputed as the start of the SB placebo run-in date.
- If end date is in the screening phase, the start date of the event is imputed as the start of the screening date.

For completely missing end dates, the event is considered to be ongoing. No imputation will be done on completely missing end dates.

Partial dates for Adverse Events and Concomitant Medications

For partial start and end dates, the minimum possible date is imputed for start date and maximum possible date is imputed for end date. For example, if partial start date is "SEP2020" and partial end date is "OCT2020" then the imputed start date is "01SEP2020" and the imputed end date is "31OCT2020".

As a conservative approach, if day was imputed for the start date and the start of the DB study treatment date has the same month, then the DB study treatment start date is used instead. For example, if partial date is "SEP2020" and the 1st dose of the DB study treatment was administered on 05SEP2020, then the partial start date is also imputed as "05SEP2020". Similarly, in case when a partial start date has both day and month imputed but the year equals the year of the 1st dose of DB study treatment date, then the partial start date is imputed as the DB study treatment start date. For example, if partial date is "2020" and DB study treatment was administered on 05SEP2020, then the partial start date is imputed as "05SEP2020".

Partial dates for Celiac Disease Diagnosis Date

For date of diagnosis of celiac disease, if both month and day are missing, they will be imputed as mid-year (i.e., July 1st). If only day is missing, the day will be imputed as the 15th of the month.

Missing date for Investigator Global Assessment

Missing dates for the Investigator Global Assessment (IGA) in the eCRF will be assumed to be the same date as other assessments captured in the eCRF for the same nominal visit.

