8.6.1.1 Primary Estimand and Handling of Intercurrent Events

The primary estimand corresponding to the primary efficacy variable consists of the following attributes:

A. Target Population

Adult patients with non-responsive celiac disease who have attempted a gluten free diet for at least 12 months as defined by the inclusion and exclusion criteria in the study protocol.

B. Endpoint

Absolute change from baseline through Week 24 in abdominal symptoms as measured by the Abdominal Symptoms domain of the CeD PRO questionnaire,

C. Population-Level Summary

Overall mean values (averaged across 24 weeks) of each of the 3 PRV-015 treatment groups compared with placebo of the change from baseline in the Abdominal Symptoms domain of the CeD PRO questionnaire.

D. Strategy for Addressing Intercurrent Events

Treatment policy strategy, i.e. all collected primary endpoint data is used regardless of intercurrent events.

Intercurrent events are events which occur after treatment initiation and may interfere with the analysis of the primary endpoint. Intercurrent events are considered to be the following:

- · Intake of prohibited medications
- · Presence of gluten

As per treatment policy strategy intercurrent events are handled by collecting all primary endpoint data following any intercurrent event.

Intercurrent event counts and timings will be summarized by treatment group. Additional analysis may be done to further explore the effect of intercurrent events.

Intake of Prohibited Medication

The number of subjects who have taken at least one prohibited medication after randomization will be tabulated by treatment group.

The time (in weeks) from randomization to the first instance of a prohibited medication will also be summarized by treatment group. This time will be calculated as (start date of first post-randomization prohibited medication – randomization date + 1)/7.

The following medications are considered prohibited medications, even if they were used to treat AEs, as indicated in the study protocol:

 Systemic or intestinal immune suppressants, including steroids. Inhaled or nasal steroids for respiratory diseases such as asthma and allergic rhinitis as well as topical steroids (except intestinal) are permitted.

- Oral pharmaceutical presentations (e.g., capsules) of probiotic supplements. Probiotics in foods (e.g., yogurt) are acceptable.
- Chronic or continuous oral and IV antibiotics (>2 weeks use). Topical antibiotic use is allowed.

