- Systemic antiviral medications
- Systemic antifungal medications
- Live vaccines (within 14 days before Study Visit 3)
- Investigational drugs

If such medication was prescribed as needed ("prn") or was taken after Visit 16, it will not be considered as an intercurrent event.

The full list of subjects who have taken a prohibited medication will be identified in a blinded manner prior to database lock and study unblinding.

Absence or Presence of Gluten

Subjects are categorized into Absence or Presence of gluten category based upon having negative stool and urine gluten tests or having positive test result for either stool or urine gluten test, respectively. If both tests are missing or one test is missing and the other one is negative the visit will be missing. If one test is positive and the other one is missing it will be presence. This will be assessed using the nominal visit for urine or stool gluten samples. Positive stool gluten test is defined as the values above $0.156~\mu g$ GIP/g. Positive urine gluten test result is defined as the values above 6.25~ng GIP/ml. Number of subjects with absence or presence of gluten will be tabulated by treatment group. Each subject could be counted in both absence and presence category at different visits.

Month	Month ending visit	Qualifying Absence	Qualifying Presence		
0	Visit 3	Stool and Urine gluten both negative at Visit	gluten positive at		
1	Visit 5	Stool and Urine gluten both negative at Visit 5	Stool or Urine gluten positive at Visit 5		
2	Visit 7	Stool and Urine gluten both negative at Visit 7	gluten positive at		
3	Visit 9	Stool and Urine gluten both			

		negative at Visit 9	
4	Visit 11	Stool and Urine gluten both negative at Visit 11	gluten positive at
5	Visit 13	Stool and Urine gluten both negative at Visit 13	gluten positive at
6	Visit 15	Stool and Urine gluten both negative at Visit 15	gluten positive at

Time (in weeks) from first dose to the first time observing the presence of gluten will also be captured for each subject. This will be calculated as (Visit date corresponding to the first presence of gluten—date of first dose of double-blind treatment + 1)/7.

Subjects having an absence or presence of gluten will be presented in a data listing.

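### The partial start-date rules in SAP 8.2.3 ignore the stop date, so an adverse event or medication that ended before first dose can be given a start after its own end

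*SAP*

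**What the plan says.** SAP 8.2.3 treats start dates of adverse events and concomitant medications in two ways.

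- **Completely missing start.** The end date decides. The first double-blind dose date is used only if the end date is missing or falls after double-blind treatment began. For an earlier end the SAP says "If end date is in the SB placebo run-in phase, the start date of the event is imputed as the start" of the run-in, with a parallel rule for screening.
- **Partial start.** The general rule is that "the minimum possible date is imputed for start date and maximum possible date is imputed for end date". A step described as conservative then overrides it. If the day is missing and first dose falls in that month, the first-dose date replaces the earliest date ("has the same month, then the DB study treatment start date is used instead"). The override also applies "in case when a partial start date has both day and month imputed but the year equals the year of the 1st dose" of double-blind treatment: "then the partial start date is imputed as the DB study treatment start date". Neither override has a stop-date condition.

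The classifications that depend on these dates are in two other sections.

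- **SAP 8.7.2.** The treatment-emergent window opens at the first double-blind dose and closes 42 days after the last. Run-in events are those that began after Visit 1 and either ended before double-blind treatment or were ongoing. They are reported separately.
- **SAP 8.5.** A prior medication both starts and stops before double-blind treatment. A concomitant one continues into that period or begins after its start. A medication whose earlier stop cannot be confirmed defaults to concomitant.

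**The concern.** Moving an uncertain start to the first dose is a sensible safeguard when the event might have begun on treatment. A known stop before first dose removes that uncertainty, yet the override still applies. The result is an impossible record, and the SAP handles it worse than a record with less information: with no start date at all, an event that ended in the run-in stays in the run-in.

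At stake is the separation of pre-dose from on-treatment adverse events, and of prior from concomitant medications. With about 55 subjects per arm, one event wrongly placed in the treatment-emergent tables moves a group's incidence by 1/55 = 1.8 percentage points. SAP 8.7.2 gives risk differences with exact intervals for serious, severe and special-interest events and for events leading to discontinuation, where counts may be low.

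**Working it through.** **Inputs.** First double-blind dose 05SEP2020 (SAP 8.2.3 example). On the Schedule of Activities, Visit 1 is 28 days earlier (08AUG2020) and screening up to 56 days earlier (11JUL2020). The stop dates below are illustrative.

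**The SAP's own figures.** Applied literally, the rules give SEP2020 → 05SEP2020 and 2020 → 05SEP2020, as the SAP states. SEP2020 with first dose in another month gives 01SEP2020, the general rule.

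**Adding a stop date.** Duration = stop − start + 1 day. The last two columns apply the override only if the stop is missing or on or after first dose.

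| Record | Start as written | Duration | Start with stop check | Duration |
|---|---|---|---|---|
| AE, start SEP2020, stop 03SEP2020 | 05SEP2020 | 3 − 5 + 1 = −1 | 01SEP2020 | 3 |
| Medication, start SEP2020, stop 04SEP2020 | 05SEP2020 | 4 − 5 + 1 = 0 | 01SEP2020 | 4 |
| Medication, start 2020, stop 20JUL2020 | 05SEP2020 | −47 + 1 = −46 | 01JAN2020 | 202 |
| Control, start SEP2020, stop 20SEP2020 | 05SEP2020 | 16 | 05SEP2020 | 16 |

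The first three records have a start after their stop under the rule as written, and none does with the check. The control does not change, so the conservative intent survives.

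**Classifying the first AE (SAP 8.7.2).** The imputed start equals the first-dose date, so it is inside the treatment-emergent window. It also lies after Visit 1 (08AUG2020), and the stop precedes double-blind treatment, so both parts of the run-in definition are met. The SAP does not say which prevails.

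**The same AE with no start date.** Its end, 03SEP2020, is in the run-in, so the start is set to the start of the run-in. It is a run-in event only.

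**Classifying the medications (SAP 8.5).** The imputed start is not before double-blind treatment, so they are not prior. They do not continue into that period, their start is on and not after its first day, and their earlier stop is confirmed, so they are not concomitant. They have no category.

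**Which records are reached.** A partial stop naming the dosing month is pushed to month end, so no contradiction arises. A partial stop naming an earlier month stays before first dose, so the problem remains.

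For the month rule, a first dose on day d of the month leaves min(d − 1, 28) of the 28 run-in days in the dosing month. That is 0 for d = 1, 4/28 = 14% for d = 5, and all 28 from d = 29. If first doses are assumed to be spread evenly over the calendar days of 2021–2024, the average is about 52%. About 96% of run-in days then share the dosing year. These are shares of days on which an exposed record could fall, not of records.

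**How far a date can move.** Adverse events are collected from consent (Protocol 8.4.1), so on schedule an adverse-event start can move by at most about 56 days. For a year-only medication, the imputed start is 248 days after the earliest possible date (01JAN to 05SEP2020). That is an upper bound, reached only by a medication begun on 1 January.

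**The case against.** The strongest reply is that the consequences are limited and partly contained. Much of it stands.

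- **A reader might infer that every such adverse event is misclassified as treatment-emergent.** The documents do not show this. The run-in definition in SAP 8.7.2 uses the end date and also captures the event. What is established is a conflict between two definitions.
- **A reader might infer that past medications become concomitant.** They do not under SAP 8.5; they are left unclassified. Nor does Protocol 6.5 require recording of a medication that ended months before screening. It asks for those in use at screening or taken during the study. Shifts of many months should therefore not be assumed typical.
- **A reader might infer that the prohibited-medication event is miscounted.** The timing formula in SAP 8.6.1.1 does use the "start date of first post-randomization prohibited medication". However, the section counts medications taken after randomization, and the subject list is drawn up blinded before database lock. Nothing says that list is generated from imputed dates with known stops ignored. The related sensitivity analysis in SAP 8.6.1.4 runs only if the evaluation of intercurrent events indicates a need.
- **A reader might also take the exemption of as-needed drugs ("If such medication was prescribed as needed") for an error.** It is a disclosed, prespecified choice on which statisticians can differ. Protocol 6.5 describes no log of individual as-needed intakes. Such use remains a protocol deviation (Protocol 6.5.1), and the per-protocol criterion in SAP 8.1.5 has no exemption. At most, the SAP could explain why its intercurrent-event definition differs.
- **Few adverse events may be exposed.** Footnote 17 of the Schedule of Activities limits pre-dose recording to procedure-related events and serious events, although Protocol 8.4.1 says all events. The serious-event report form also asks for the onset date (Protocol 10.2.4), so partial starts should be less common there.

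None of this supplies the missing condition or justifies leaving it out.

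**Conclusion.** The point holds as a narrow defect. Both partial-date overrides omit the stop-date check that the rule for completely missing dates contains. A record whose stop precedes first dose can therefore receive a start after its own end. For an adverse event the result is a conflict between the treatment-emergent and run-in definitions; for a medication, a record outside both categories.

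The size cannot be computed, because the documents give no count of partial dates. It is probably small, since it needs a partial start, a matching month or year, and a stop before first dose. The primary estimate is not affected: it does not use these dates, and under the treatment-policy strategy all collected scores are kept. The conclusion rests on a literal reading of SAP 8.2.3. A programmer might add the check unprompted, but the plan does not ask for it.

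**What to change.** In both partial-date rules of SAP 8.2.3, apply the first-dose substitution only if the end date is missing or, after its own imputation, falls on or after the first double-blind dose. Otherwise keep the earliest possible start date. The cost is one clause in each rule and a matching line in the date-derivation program, with no new data. Records that might have begun on treatment are handled as now.

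Optionally, one sentence in SAP 8.6.1.1 could give the reason for exempting as-needed prohibited medication from the intercurrent event.

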8.2.4 Handling of Data from Discontinued Subjects

Generally, the data from subjects who discontinue the study will be presented up to the point of discontinuation. Subjects who discontinue the study prior to randomization will not be included in ITT, mITT, PP or safety analysis set. Subjects who permanently discontinue the treatment will be included in the analysis set(s) based on the analysis set inclusion definition.

A subject who permanently discontinues treatment will be encouraged to return for all subsequent on-site visits as listed in the SoA (Appendix 11.1), i.e., Visits 4, 5, 7, 9, 11, 13, 14, 15, and 16. If the discontinued subject chooses to not return for on-site visits, the Early Termination (ET) visit should be done and subject is asked to return 6 weeks after the last dose of the study drug for the final safety follow-up visit.

If subject decides to permanently discontinue the study, the early termination assessments listed for Visit 15 (Week 24) should be conducted before the withdrawal, including EGD and biopsy, unless the withdrawal occurs before randomization.

8.3 Disposition of Subjects, Analysis sets, and Major Protocol Deviations

Disposition of subjects includes the following tabulations of subjects by treatment, where appropriate:

- Screened
- Screen failures
 - Failed initial screening
 - Re-screened and failed re-screening
- Entered single-blind placebo run-in phase, not dosed
- · Treated with single-blind placebo in run-in phase
- Failed during the run-in phase
- Discontinued during the run-in phase, including reason
- Randomization failures
- Randomized
- Randomized, not dosed
- · Treated with double-blind treatment
- Discontinued the double-blind treatment, including reason
- Discontinued the study, including reason
- Completed the study

Screen failures are defined as subjects who consent to participate in the clinical study but do not enter the single-blind placebo run-in phase.

Run-in failures are defined as those who enter the single-blind placebo run-in phase but do not continue past Visit 2 of the run-in phase.

Randomization failures are defined as those who enter the single-blind placebo run-in phase but do not meet the inclusion criteria at Visit 3 and therefore are not randomized to a treatment group.

The number and percentage of subjects in each analysis set will be summarized by treatment group. Disposition will also be summarized by country and site.

Major protocol deviations will be summarized by treatment group for the ITT analysis set.

Disposition of subjects, inclusion/exclusion criteria not met, informed consent dates, randomization information, protocol deviations and run-in, treatment, and study discontinuations will also be listed by subject.

Disposition is done on the ALL analysis set.

8.4 Demographic and Baseline Characteristics

Demographic and baseline characteristics include:

- Age (years) at initial screening
- Sex
- Race
- Ethnicity
- Weight (kg)
- Height (cm)
- BMI (kg/m²)
- Stratification factor from IRT system: VH:CD of <2 or ≥2
- Stratification factor from IRT system: CeD PRO Abdominal Symptoms domain score of <3 or ≥3
- GSRS at screening
- Time since celiac disease diagnosis (months), calculated as (Date of randomization Date of celiac disease diagnosis)/30.4375
- Anti-tTG Antibodies IgG
- Anti-DGP Antibodies IgG

Demographics and baseline characteristics are assessed at screening or prior to randomization (stratification variables). Demographic and baseline characteristics will be listed and summarized by treatment group. Demographics and baseline characteristics are presented on mITT, ITT, and PP (if applicable) analysis set. Efficacy and safety baseline characteristics not presented here are presented in the respective efficacy and safety tables.

Demographic information, baseline characteristics, and other information (e.g., HLA-DQ at Screening) will be provided in data listings.

8.5 Prior and concomitant medications and medical history

Prior and concomitant medications will be collected throughout the study. Medications will be coded using the latest WHO Drug dictionary available at the time of the database lock.

Prior medications are those which start and stop prior to the start of double-blind treatment. Concomitant medications are those which continue into the double-blind treatment period or begin after the start of double-blind treatment. Any medication that cannot be confirmed as stopping before the start date of the double-blind period will be classified as a concomitant medication.

Concomitant medications will be summarized by ATC 1, preferred name, and treatment group. All prior and concomitant medications will be listed for the ITT analysis set.

Medical history will be coded using the latest Medical Dictionary of Regulatory Activities (MedDRA) available at the time of the database lock. Medical history will be collected during screening and summarized by dose and overall total by system organ class and preferred term, on the mITT analysis set. Summaries will be ordered by descending order of the overall incidence of system organ class and preferred term within each system organ class.

Medical history conditions, will be presented on a by-subject listing, using the ITT analysis set.

Treatment Compliance

Treatment compliance (%) will be estimated and presented for the double-blind treatment period in the mITT analysis set. Compliance for a subject will be performed as [total number injections received]/[total planned number of injections]*100.

Total number injections received = Number of injections summed from the Study Drug Administration eCRF page over Visits 3 through Visit 14

Total planned number of injections = (Number of planned visits in double-blind period from Visit 3 through the earlier of Visit 14 and Study Discontinuation)*4

Summary statistics of treatment compliance will be provided by treatment group. The number and percentage of subjects in each category of treatment compliance (<80%, 80-<100%, 100%, >100%) will be presented by treatment group.

Treatment compliance will also be provided in a data listing for mITT analysis set.

